### *Exclusion criteria*

- i. Guards with complications in co-morbid conditions like Diabetes, Cirrhosis, etc.
- ii. Guards of age less than 20 or more than 60 years.
- iii. Guards who do not consent to be a part of this study.
- iv. Guards who fail to comply with the yoga protocol in Intervention Group.

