#### Key questions expected to be answered by this study:

- a) What are the effects of yoga on biochemical and molecular markers of stress leading to changes in DNA damage response
- b) Is there any change in the DNA repair capacity of yoga-practicing subjects as compared to matched controls?
- c) What will be the mechanism by which yoga modulates DNA damage response and repair.

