### Methodology

Recruitment of individuals: Department of Police, Chandigarh has agreed to help us on this aspect. Policemen working for Chandigarh Police will be chosen based on the inclusion and exclusion criteria.

Subjects: Those security guards (age: >20 and <60) who are willing to consent to participate in this study will be screened for moderate and higher stress on Cohen's PSS, according to inclusion criteria and randomly divided between Intervention (Yoga Group) and Control Group.

Sample Size: The sample size of 206 was calculated for 99% confidence level (reliability coefficient = 2.58), at the alpha level of 0.05, a power of 0.95, and a relative precision of 0.2, derived from a pilot study done on breast cancer patients and yoga practitioners (Ram et al, 2013). Assuming a 10% drop out rate, a total of 229 subjects will be recruited.

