### Flow Chart 3: Allocation of Sample Size According to Consort Guidelines

### *Inclusion criteria*

- i. Guards scoring more than 15 points on Cohen's scale. Once these subjects' consent to enroll, each one of them will be coded to maintain anonymity.
- ii. Both males and female guards of age 20 to 60 years.

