### **Variables**

- Socio-demographic details – age, diet, alcohol consumption, etc.
- Evaluation of stress level on Cohen's Perceived Stress Scale (pre and post intervention) (Cohen, Kamarck & Mermelstein, 1983)
- Evaluation of stress level using vital parameters: Blood pressure and resting heart rate of participants will be recorded pre and post intervention.

- Evaluation of stress level using molecular parameters: (pre and post intervention) 10 ml of blood will be withdrawn from the subjects by trained phlebotomists, and coded. WBCs and plasma will be separated using standard protocols and stored at -80°C. Plasma will be utilized to assess the levels of cortisol.
- Assessment of chromosomal translocations: (pre and post intervention) Genomic DNA will be extracted from WBCs isolated, and tested for chromosomal translocations using PCR assay. Isolated genomic DNA will be subjected to nested PCR using primers specifically designed to check for t(14;18) and t(11;14) translocations.
- Assessment of DDR and DNA repair:
- *Immunofluorescence*: Isolated PBMCs will be subjected to DDR analysis by immunofluorescence. For this, these cells will be fixed and stained with various DDR markers like γH2AX, 53BP1, pATM.
- *Gene expression analysis*: Total RNA will be isolated from these cells; cDNA will be synthesized and the expression of following DDR and DNA repair genes will be performed using real-time PCR: RAD51, MRE11, RAD50, NBS1, KU70, LIGASE IV, PARP1
- *Comet assay*: Cells will be used to perform both the neutral as well as alkaline comet assay to assess for the number of single- and double-strand breaks.
- Telomeric length: Relative telomere length (TL) using quantitative polymerase chain reaction (qPCR) will be performed on genomic DNA isolated from control and group blood samples and will be compared.

Time Line for experiments:

S.No.	Experiments	Time point
1.	Cortisol levels	0 day
2.	DDR: Immunofluorescence for γH2AX, 53BP1, and ATM.  Gene expression analysis for KU70, LIGASE IV, RAD51,	0 day

	PARP1, MRE11, RAD50, NBS1	
3.	Nested PCR for Chromosomal Translocations	0 day
4.	DNA repair: Comet assay	0 day
5.	Cortisol levels	3 months
6.	DDR: Immunofluorescence for $\gamma$ H2AX, 53BP1, and ATM.  Gene expression analysis for KU70, LIGASE IV, RAD51,  PARP1, MRE11, RAD50, NBS1	3 months
7.	Nested PCR for Chromosomal Translocations	3 months
8.	DNA repair: Comet assay	3 months

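### The eligibility criteria do not exclude guards who already practise yoga or meditation, so the yoga-versus-control contrast may be attenuated by an unknown amount

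*Protocol*

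**What the plan says.** The Protocol has two inclusion criteria: "Guards scoring more than 15 points on Cohen's scale" and "Both males and female guards of age 20 to 60 years". It has four exclusions: "Guards with complications in co-morbid conditions like Diabetes, Cirrhosis, etc"; age outside the range; no consent; and "Guards who fail to comply with the yoga protocol in Intervention Group". The last is the only criterion that mentions yoga, and it concerns adherence after allocation to one arm.

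Under Methodology, eligible guards are "randomly divided between Intervention (Yoga Group) and Control Group". The readable text does not say what the control group does, or does not do, for the 3 months.

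Two stated aims depend on a clean contrast. Key question b asks "Is there any change in the DNA repair capacity of yoga-practicing subjects as compared to matched controls". Objective 1, repeated in SAP section 2, compares the molecular markers at baseline with those after the yoga period.

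The Variables section opens with "Socio-demographic details – age, diet, alcohol consumption, etc" and goes on to stress score, vital signs and laboratory measures. Yoga or meditation practice is not named. In the time schedule (first year, item D), the follow-up described is for adherence to the yoga protocol; no counterpart for controls appears.

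**The concern.** A guard who has practised yoga for years satisfies every written criterion. Allocated to yoga, this guard gives a day-0 sample that already reflects practice, so the change over 3 months may understate what the programme does for a newcomer. Allocated to control, the same guard is a practising subject on the side of key question b that is meant to supply the comparison. Both effects pull the estimated difference towards zero. Control guards who take up yoga during the 3 months would do the same.

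What is at stake is how a null or weak result is read. Unless practice is recorded in both arms, it would be hard to separate an ineffective programme from a comparison in which some controls were also practising.

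**Working it through.** **1. Applying the criteria.** Take a consenting guard within the age range, scoring above 15, without co-morbid complications, who practises yoga regularly. Both inclusion criteria are met. The exclusions for co-morbidity, age and consent do not apply, and the fourth cannot apply before allocation. The guard is eligible for either arm.

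**2. Effect on the contrast.** Let δ be the mean effect of the programme on a guard who does not practise, and p the fraction who already do. Assume, as the worst case, that existing practisers gain nothing further. Apart from any time trend common to both arms:

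- expected change, yoga arm: (1 − p)·δ + p·0 = (1 − p)·δ
- expected change, control arm: 0
- difference between arms: (1 − p)·δ

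The change within the yoga arm shrinks by the same factor. Random allocation makes p equal in the two arms on average, so nothing shifts the comparison in favour of yoga.

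**3. The plan's own figures.** Methodology gives 206 evaluable guards, alpha 0.05, power 0.95, a 99% confidence level (2.58), relative precision 0.2 and 10% dropout. The recruitment figure reproduces: 206/0.90 = 228.9, rounded up to 229. The 206 can be neither confirmed nor refuted, because no mean, SD, proportion or effect size is given. The precision formula gives (2.58/0.2)² × CV² = 166.4 × CV², which equals 206 only if CV = 1.11. Read instead as a two-arm comparison with 103 per arm (1:1 is an assumption) and 95% power at two-sided 0.05, it implies a standardised difference of (1.960 + 1.645) × √(2/103) = 0.502, which the Protocol does not state.

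**4. Power under dilution.** Taking 0.95 as the power of the between-arm test, with variance unchanged:

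Power = Φ((1.960 + 1.645)(1 − p) − 1.960)

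The evaluable number that would restore 95% power is 103/(1 − p)² per arm, rounded up and doubled.

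| p (assumed) | Argument of Φ | Power | Evaluable N for 95% power |
|---|---|---|---|
| 0 | 1.645 | 95% | 206 |
| 5% | 1.465 | 92.8% | 230 |
| 10% | 1.285 | 90.0% | 256 |
| 20% | 0.924 | 82.2% | 322 |
| 30% | 0.564 | 71.3% | 422 |

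If a fraction c of the non-practising controls also started yoga and gained the full effect, the factor would be (1 − p)(1 − c). With p = c = 10% it is 0.81, and power is Φ(3.605 × 0.81 − 1.960) = Φ(0.960) = 83.1%. The documents give no value for p or c.

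**5. Could the analysis repair this?** The Per-Protocol Set (SAP section 3) and the optional sensitivity analysis (SAP section 8) remove participants with protocol deviations. With no readable rule against it, prior practice or practice by a control is not a deviation, so these guards would stay in every analysis set. SAP section 6 lists two-group tests, ANOVA-type tests and correlations, with no covariate or subgroup for yoga practice.

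**The case against.** The strongest counter-argument is that broad eligibility is a legitimate choice. Randomisation balances prior practice on average, and a result for guards as they are serves the Project summary's aim of helping the police department. This stands in part: there is no systematic bias favouring yoga, and the proposed exclusion does narrow applicability. It does not remove the attenuation, and it is no reason to leave practice unrecorded.

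The power figures can also be challenged, fairly. The programme is a specific module given 5 days a week for 13 weeks, and a guard's existing habit need not equal it; any further gain makes the loss smaller than p. The sample-size statement mixes precision and power language, so 0.95 is not shown to belong to a between-arm test. The values of p have no basis in the documents.

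Four stronger readings are tempting, and the documents support none of them:

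- **That the contrast is diluted.** No prevalence of practice or rate of control uptake is given. Working in one police department makes uptake possible but does not show it.
- **That the plan gives controls no instruction.** The work plan figure, the allocation flow chart, most of the yoga module listing and the consent pages could not be read. This part rests on the readable text only. The eligibility lists are complete, and that part does not depend on the missing material.
- **That practice could not be checked afterwards.** The list of socio-demographic items is open-ended and might include it.
- **That the sample-size source shows practisers must be kept apart.** The Protocol says only that the figure was "derived from a pilot study done on breast cancer patients and yoga practitioners". How that pilot used its groups is not described, and the other group named is cancer patients, not non-practising controls.

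**Conclusion.** The point holds for eligibility: as written, the criteria admit existing yoga or meditation practisers to both arms, and the SAP's analysis sets would not remove them. The between-arm contrast in key question b and the baseline-to-3-month comparison in Objective 1 may be attenuated by an amount the documents do not allow anyone to estimate. The consequence is lost power and a null result that is harder to interpret, not an exaggerated benefit of yoga.

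The illustrated loss, from 95% to between 93% and 71% for p of 5% to 30%, is the worst case for prior practice alone. It rests on three assumptions: existing practisers gain nothing, 0.95 is the power of the two-sided 0.05 between-arm comparison, and variance is unchanged. Uptake by controls would add to it. The change is worth making because it is cheap and protects the contrast on which the trial is built; the gap does not invalidate the design.

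**What to change.** 1. Add to the Exclusion criteria, applied before randomisation, regular yoga, pranayama or meditation practice within a look-back period that the investigators state.
2. Describe the control condition, including a request that control guards not start yoga until the 3-month sample has been taken. If such an instruction already exists in material that could not be read, repeat it in the Protocol's main text.
3. Add one question on yoga and meditation practice to the existing questionnaire, asked at day 0 and at 3 months in both arms. Name it in the Variables section, and state in the SAP that control-arm uptake will be reported with the main result.

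The cost is one eligibility line, one instruction and one questionnaire item. The downside is a slightly smaller pool of eligible guards, and results that apply to guards not already practising. If the investigators prefer to keep eligibility broad, items 2 and 3 alone would still make the result easier to interpret, although they would not recover the power lost to prior practice.

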### **Design of the study**

In a randomized control trial (RCT), participants are allocated randomly between intervention and control groups to compare the treatments, which enables statistical control over the influences imparted by the aforementioned treatments. In the present study, the policemen who satisfy our eligibility criteria and willing to consent to participate in our study will be enrolled, grouped randomly in intervention and control groups, and assessed for the dependent variables of the study before and after the Integrated Yoga intervention period.

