**Total duration in weeks/months for yoga therapy: 3 months (13 Weeks: 5 days a week)**

### **Time schedule of activities giving milestones**

#### First year:

- A. Recruit policemen and get them to fill a questionnaire in order to identify most stressed individuals.
- B. Obtain blood samples, isolate PBMCs, serum and plasma. Biochemical analysis to test for cortisol levels will be performed.
- C. The subjects will be given yoga training for 3 months along with studying DNA damage response and repair using comet assay, immunofluorescence and real-time PCR.
- D. Follow up of the subjects to ensure compliance for yoga protocol.

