Date: February 29, 2020

NCT number: Not

Available

Official Project Title

Investigating the Role of Yoga in Alleviating
Chromosomal Translocations in Security Guards
of Chandigarh Police Who Are Responsible for
the Safety of VIPs

Statistical Analysis Plan (SAP)

1. Introduction

This Statistical Analysis Plan (SAP) outlines the planned analyses for the study titled “Investigating the Role of Yoga in Alleviating Chromosomal Translocations in Security Guards of Chandigarh Police Who Are Responsible for the Safety of VIPs”. It defines the methods for analyzing study endpoints, including descriptive, inferential, and correlation analyses.

2. Objectives and Endpoints

1. Analysis of molecular markers related to DNA damage response and repair before and after the practice of yoga on Chandigarh Police.
2. To examine the molecular mechanism by which yoga may modulate DNA damage response and repair.

3. Analysis Populations

- **Full Analysis Set (FAS):** All participants meeting eligibility criteria and providing baseline and outcome data.
- **Per-Protocol Set (PPS):** Subset of participants completing the study without major protocol deviations.

4. General Statistical Considerations

- All analyses will be conducted using **GraphPad Prism v8.0.2** and **JASP v0.19.3**.
- Two-sided significance level of $\alpha = 0.05$ will be applied.

- Adjusted p-values from post hoc tests will also use the **0.05 threshold** for significance.
- Continuous variables will be summarized with **mean \pm SD** (if normally distributed) or **median with interquartile range** (if non-normal).
- Categorical variables will be summarized as **frequencies and percentages**.

5. Assessment of Assumptions

- **Normality:** Assessed using the **Shapiro-Wilk test**.
- **Homogeneity of variance (ANOVA assumption):** Checked using **Levene's test**.

6. Statistical Methods

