6.1 Comparisons of Two Groups

- **Normally distributed data:** Student's *t*-test (paired or unpaired as appropriate).
- **Non-normal data:** Wilcoxon matched-pairs signed rank test (paired) or Mann-Whitney test (independent).

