6.3 Correlation Analyses

- **Normally distributed data:** Pearson's correlation coefficient.
- **Non-normal data:** Spearman's rank correlation coefficient.

7. Handling of Missing Data

- Data will be analyzed as observed (complete case analysis).
- No imputation will be performed unless otherwise specified in the protocol.

8. Interim and Sensitivity Analyses

- No interim analyses are planned.
- Sensitivity analyses may be conducted to confirm robustness of results (e.g., excluding participants with protocol deviations).

9. Reporting

- Results will be presented in accordance with **CONSORT/CONSORT-Extension guidelines**.
- Statistical outputs will include effect sizes, 95% confidence intervals, and exact p-values.

Principal Investigator

[name]

Additional Professor

Department of Experimental Medicine and Biotechnology

PGIMER, Chandigarh

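### Non-compliance in the yoga arm is listed as an exclusion criterion, so the Full Analysis Set as written drops non-compliers from one arm after randomisation

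*Protocol*

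**What the plan says.** Protocol, Exclusion criteria, item iv, excludes "Guards who fail to comply with the yoga protocol in Intervention Group". The list has no counterpart for controls, and the readable text does not say how much missed practice counts as failure.

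Protocol, Design of the study, puts eligibility first and allocation second: "the policemen who satisfy our eligibility criteria and willing to consent to participate in our study will be enrolled, grouped randomly". The yoga programme then runs for 13 weeks at 5 days a week. The first-year schedule includes "Follow up of the subjects to ensure compliance for yoga protocol", so compliance is observed during the intervention.

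SAP section 3 defines two sets. The FAS is "All participants meeting eligibility criteria and providing baseline and outcome data". The PPS is "Subset of participants completing the study without major protocol deviations". The SAP assigns no comparison to either set and defines no set of all randomised participants. Section 8 offers, as an optional sensitivity analysis, "excluding participants with protocol deviations".

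**The concern.** An eligibility criterion has to be decidable before allocation. Item iv is not: it depends on which arm the guard was assigned to and on what he or she did over the next three months. Because the FAS depends on eligibility, the criterion carries into the main analysis set and acts on one arm only.

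Guards who do not keep up the programme may differ from those who do, for example in stress or alcohol use, both of which the protocol records. The yoga arm would then consist of compliers, while the control arm would still contain the guards who would not have complied. The difference between arms mixes any yoga effect with that selection. It could create an apparent benefit or hide a real one, and a larger sample would not remove it.

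**Working it through.** **Text.** Set side by side, the passages give this sequence:

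1. Eligibility is satisfied, then guards are randomised (Protocol, Design of the study).
2. Compliance is observed over 13 × 5 = 65 practice days (Protocol, total duration of yoga therapy, and First year, item D).
3. Failure to comply in the yoga arm is an exclusion (Protocol, Exclusion criteria, iv).
4. The FAS requires eligibility (SAP 3).

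Steps 1 and 3 contradict each other. Steps 3 and 4 together remove yoga non-compliers from the FAS. With no threshold over the 65 days, the number removed is open.

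**The plan's own figure.** "Assuming a 10% drop out rate, a total of 229 subjects will be recruited": 206/0.9 = 228.9, rounded up to 229. This reproduces. The 10% is the only attrition figure in the documents, and it is for drop-out, not non-compliance.

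**Illustration of size, literal reading, no yoga effect.** Assumptions not in the documents:

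- 1:1 allocation, so 206/2 = 103 per arm.
- An unpaired *t*-test on 3-month values, two-sided 0.05. SAP 6.1 says only "paired or unpaired as appropriate".
- Outcome mean 0 and SD 1 in each arm as randomised.
- A share *q* would not comply, with a mean *d* SD worse than compliers.

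For the overall mean to be 0, compliers average *qd* better than the whole arm and non-compliers (1 − *q*)*d* worse. Removing non-compliers from the yoga arm only therefore gives:

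- bias = *q* × *d*
- variance among those kept = 1 − *q*(1 − *q*)*d*²
- SE = √(1/103 + variance kept / number kept)

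Type I error comes from the noncentral *t* distribution with noncentrality bias/SE. Worked case, *q* = 0.1 and *d* = 0.5: 93 guards kept, bias 0.050, variance 1 − 0.09 × 0.25 = 0.9775, SE = √(1/103 + 0.9775/93) = 0.142, noncentrality 0.050/0.142 = 0.35, type I error 6.4%.

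| Removed from yoga arm | Gap *d* (SD) | Bias (SD) | Type I error |
|---|---|---|---|
| 10% (93 kept) | 0.2 | 0.020 | 5.2% |
| 10% | 0.3 | 0.030 | 5.5% |
| 10% | 0.5 | 0.050 | 6.4% |
| 10% | 0.9 | 0.090 | 9.8% |
| 20% (82 kept) | 0.2 | 0.040 | 5.8% |
| 20% | 0.3 | 0.060 | 6.9% |
| 20% | 0.5 | 0.100 | 10.4% |
| 20% | 0.9 | 0.180 | 24.1% |

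Simulation (40,000 trials per setting) for gaps of 0.2, 0.5 and 0.9 SD agrees: 5.1%, 6.2% and 9.6% at 10% removed, and 5.6%, 10.6% and 23.4% at 20%. With nobody removed it gave 4.7% to 5.3%.

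With 229/2, about 115 per arm, gaps of 0.2 to 0.5 SD give about 5.3% to 6.6% (10% removed) and 5.9% to 11.1% (20% removed). To reach a 10% type I error with 103 per arm, the gap must be 0.92 SD at 10% removed or 0.48 SD at 20% removed.

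**Change scores.** The gap is 0.2 to 0.5 SD at 3 months, with an assumed pre-post correlation of 0.3 to 0.7 and 103 per arm. The bias is *q* × (gap at 3 months − gap at baseline).

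| Gap at baseline | 10% removed | 20% removed |
|---|---|---|
| Same as at 3 months | 5.0% | 5.0% |
| Half as large | 5.0% to 5.6% | 5.2% to 7.2% |
| None | 5.2% to 7.4% | 5.6% to 14.3% |

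**The case against.** The best defence is that nobody intended this.

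- The SAP has a separate PPS for participants without major deviations.
- Its sensitivity analysis drops deviators, which would do little for yoga attendance if non-compliers had already left.
- The protocol's design section uses eligibility for what is settled before allocation.

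On that reading, item iv is a drafting slip, non-compliers stay in the FAS, and the one-arm bias does not arise there. In addition, the work plan figure and the allocation flow chart cannot be read in the available text and might show how non-compliers are counted. The illustrative inflation is also slight at 10% removed with a moderate gap, and every input to it is assumed.

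Much of this stands. The softer reading is plausible, and the numbers do not show a large bias. But no readable passage adopts that reading. A PPS and a sensitivity analysis can coexist with a FAS that already lacks yoga non-compliers, because other deviations remain. The contradiction between item iv and the design section exists on either reading. Modest illustrative figures do not put a bound on the bias, since the documents give neither the non-compliance rate nor its link to outcome.

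**Conclusion.** The concern holds. The rule is wrong as written: a post-randomisation, one-arm condition sits among the eligibility criteria, and the FAS inherits it. That is certain from the text. Whether the analysis would in fact drop these guards depends on which reading the analyst adopts, and the readable text leaves that open.

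On the literal reading, and under the stated assumptions, inflation for 3-month values is slight at 10% removed with a moderate gap (up to about 6.4%). It roughly doubles the nominal 5% at 20% removed with a 0.5 SD gap. Change scores lessen it, and remove it where the baseline gap equals the 3-month gap; if there is no baseline gap it can be larger, up to about 14.3%. The sign reverses if non-compliers have the better values. It must be fixed because the validity of the randomised comparison should not depend on how an analyst reads one word.

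**What to change.** - **Protocol, Exclusion criteria:** delete item iv, so that eligibility is settled before randomisation as the design section already says.
- **SAP 3, FAS:** define it as all randomised guards, analysed in their assigned arm whatever their yoga attendance, using all available outcome data. Name it as the set for the between-arm comparisons.
- **SAP 3, PPS:** use compliance only here, as a secondary analysis, with the attendance threshold written down before outcome data are seen.
- **Follow-up:** seek the already planned 3-month blood sample and perceived-stress score from guards who stop attending.

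The cost is a wording change in both documents plus some effort to reach non-attenders; no assay or visit is added. Two downsides remain. The estimated effect may be diluted by non-compliers, and guards with no 3-month value still drop out of the planned complete-case tests, which is a separate matter. If the softer reading was intended, the analysed guards change little and the gain is that the rule becomes explicit.
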